Study Arm	Part A	Doses in P304 Part A	Part A Dose	Move on to Part B?	Part B	Doses in P304 Part B	Part B B-Dose	Total Doses in P304
SOT Recipient Cohorts								
Unvaccinated participants who consent to receive only 2 doses in Part A (Days 1 and 29)	Group A1	2	100 µg		NA	N/A	N/A	2
Unvaccinated participants who consent to receive 3 doses in Part A (Days 1, 29, and 85)	Group A2	3	100 µg	➡	Group B2	1	100 µg	4
Participants previously vaccinated with 2 doses of the Moderna COVID-19 vaccine under the EUA who consent to receive a third dose in Part A (Day 1)	Group A3	1	100 µg	➡	Group B3	1	100 µg	2
SOT recipients who completed primary vaccination with an mRNA or non-mRNA COVID-19 vaccine outside mRNA-1273-P304 who consent to receive 1 booster dose (in Part B)	N/A	N/A	N/A		Group B4	1	100 µg	1

Study Arm	Part A	Doses in P304 Part A	Part A Dose	Move on to Part B?	Part B	Doses in P304 Part B	Part B B-Dose	Total Doses in P304
Healthy Adult Cohort								
Healthy adults who consent to receive 2 doses in Part A (Days 1 and 29)	Group A5	2	100 µg	➡	Group B5	1	100 µg	3

[figure not shown]
Abbreviations: B-Dose = booster dose; EUA = Emergency Use Authorization; SOT = solid organ transplant,

Figure 1: Study Schema for Unvaccinated Participants Who Receive the 2-Dose Vaccination Regimen (Part A)

[figure not shown]
Abbreviations: CMI = cell-mediated immunity; IA = interim analysis; immuno = immunogenicity; NP = nasopharyngeal; SOT = solid organ transplant (recipients).

Figure 2: Study Schema for Unvaccinated Participants Who Receive the 3-Dose Vaccination Regimen (Part A)

Abbreviations: CMI = cell-mediated immunity; NP = nasopharyngeal; SOT = solid organ transplant (recipients).

**Figure 3: Study Schema for Previously Vaccinated Participants Who Receive a Single-dose Vaccination Regimen (dose 3)
(Part A)**

Abbreviations: CMI = cell-mediated immunity; NP = nasopharyngeal; SOT = solid organ transplant.

Figure 4: Booster Phase Study Pathway

[figure not shown]
[figure not shown]

Figure 5: Study Schema for Booster Dose Phase (Part B)

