6.2. Discontinuing Study Vaccination

Participants can discontinue study injection (ie, refuse the second or third dose) for any reason, without prejudice to further treatment the participant may need to receive.

The investigator, in consultation with the Sponsor's medical monitor, may withhold a participant from further injection if the participant does any of the following:

- Withdraws consent to participate in the study ([Section 6.3](#))
- Becomes pregnant ([Section 7.5.5](#))
- Develops, during the course of the study, symptoms or conditions listed in the exclusion criteria ([Section 4.1.1.2](#) or [Section 4.1.2.2](#))

- Experiences an unsolicited AE (other than reactogenicity) after injection that is considered by the investigator to be related to vaccine ([Section 7.5.10](#)) and is assessed as severe ([Section 7.5.9](#))
- Experiences an AE or SAE that, in the judgment of the investigator, requires vaccine withdrawal due to its nature, severity, or required treatment, regardless of the causal relationship to vaccine
- Experiences a clinically significant change in vital sign measurements or general condition that, in the judgment of the investigator, requires vaccine withdrawal
- Experiences anaphylaxis ([Section 7.5.5](#)) clearly related to vaccine
- Experiences an event that meets the criteria for study pause rules ([Section 7.6.2](#))

The reason(s) for withdrawal from further injection will be recorded in the eCRF.

If a participant takes a prohibited drug therapy, the investigator could withhold the second or third dose based on a joint decision of the investigator and the CRO's medical monitor ([Section 5.5.2](#)).

Every reasonable attempt will be made to follow-up with participants for safety throughout the entire scheduled study period according to their regimen, even if the participant does not receive the second or third dose or misses 1 or more visits. Unless participants withdraw consent, they are expected to remain in the study and complete all scheduled visits and assessments.

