- Imputation rules for missing AE dates are provided in [Appendix C](#).
- For laboratory assessments, if the majority of results are indefinite, imputation of these values will be considered. If the laboratory results are reported as below the LLOQ (e.g., <0.1), the numeric values will be imputed by  $0.5 \times \text{LLOQ}$  in the summary. If the laboratory results are reported as greater than the ULOQ (e.g., >3000), the numeric values will be imputed by ULOQ in the summary.
- For immunogenicity assessments, imputation of missing results will be considered based on description in [Section 6.4](#).
- Other incomplete/missing data will not be imputed, unless specified otherwise.

**Participant groups** will be summarized according to the schema below.

- Transplant status:
  - SOT Kidney
  - SOT Liver
  - SOT Total
  - 2-Dose Healthy
- Dosing regimens:
  - Overall
  - Unvaccinated SOTs Who Received 2 Doses
  - Unvaccinated SOTs Who Received 3 Doses
  - Previously Vaccinated SOTs Who Received a Third Dose
  - Total SOTs Who Received 3 Doses
  - Primary Series All SOTs Who Received a Booster Dose
- Primary Series All SOTs Who Received a Booster Dose:
  - Overall
  - 3-Dose Moderna
  - 3-Dose Pfizer

Confidential

- Other

Unless otherwise mentioned, the results of the analyses will be summarized according to the participant groups above. Subjects under the same dosing regimen may be combined for analyses regardless of BD. Participants that received booster may be analyzed separately from participants that did not receive booster.

**Subgroup analyses** for safety and immunogenicity endpoints may be analyzed in select subgroups specified below as applicable:

- Age (18 to < 65,  $\geq$  65)
- Time of post-transplantation (< 2,  $\geq$  2 years)
- Baseline SARS-CoV-2 Status in each part (Positive, Negative) (for safety data)
- Sex (Male, Female)
- Race (White, Communities of color)
- Anti-metabolite immunosuppression (Yes, No)
- Combination of immunosuppressants (Mycophenolate, Tacrolimus, and Prednisone; Mycophenolate and Tacrolimus; Tacrolimus; and Other)
- Previous induction therapy (Basiliximab or other monoclonal antibody; Basiliximab or other monoclonal antibody with steroids; Thymoglobulin; Thymoglobulin with steroids; or steroids alone)

All analyses will be conducted using SAS Version 9.4 or higher.

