### **6.3.1. Adverse Events**

Unsolicited AEs are collected for the purpose of assessing safety. All safety analyses will be based on the Safety Set.

A treatment-emergent AE (TEAE) is defined as any event occurring during the study not before exposure to study vaccine or any event already present that worsens after exposure to study vaccine. Worsening of a pre-existing condition after vaccination will be reported as a new AE.

Adverse events will also be evaluated by the investigator for the coexistence of MAAE which is defined as an AE that leads to an unscheduled visit to a healthcare practitioner.

Unsolicited AEs will be coded by PT and SOC using MedDRA and summarized by participant group and analysis stage (up to 28 days after any vaccination and throughout the study period from Day 1 (Part A)/BD-Day 1 (Part B)/Day 1 (Part A and Part B); see [Section 6.1](#) for definitions of participant group and analysis stage).

Similarly, adverse events related to organ rejection status will be reviewed by an adjudication committee as described in Section 7.6.1 of Protocol Amendment 4 to determine whether they represent an adjudicated biopsy-proven organ rejection. Events that are adjudicated as biopsy-proven organ rejection will be summarized for transplant recipients by participant group and analysis stage. Adjudication results will be listed.

All summary tables (except for the overall summary of AEs) for unsolicited AEs will be presented by SOC and PT for TEAEs with counts of subjects included. SOC will be displayed in internationally agreed order. PT will be displayed in descending order of frequency, overall, and then alphabetically within SOC. When summarizing the number and percentage of subjects with an event, subjects with multiple occurrences of the same AE or a continuing AE will be counted once. Subjects will be presented according to the highest severity (the strongest relationship) in the summaries by severity/grade (of related AEs), if subjects reported multiple events under the same SOC and/or PT.

Percentages will be based upon the number of subjects in the Safety Set within each participant group.

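### Read literally, the SAP's Day 1 safety columns for unvaccinated transplant recipients depend on doses later received, so an event that stops dosing before Day 85 cannot appear in the 3-dose column

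*SAP*

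**What the plan says.** The safety of the 2-dose and 3-dose regimens is a Part A primary objective (Protocol Table 1; SAP 2.1). Its endpoints run from Day 1 and include adverse events that lead to stopping dosing, and biopsy-proven rejection (SAP 3.1).

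The SAP builds the columns as follows.
- SAP 6.1 lists "Unvaccinated SOTs Who Received 2 Doses" and "Unvaccinated SOTs Who Received 3 Doses" among the dosing regimens. Unless stated otherwise, "the results of the analyses will be summarized according to the participant groups above".
- SAP 6.3.1 applies the columns to rejection: "Events that are adjudicated as biopsy-proven organ rejection will be summarized for transplant recipients by participant group and analysis stage". It sets the denominator: "Percentages will be based upon the number of subjects in the Safety Set within each participant group".
- One dose is enough to enter the Safety Set (SAP 5.1), and both Part A analysis stages open at the first injection (SAP 6.1).
- The same list also has Overall, kidney, liver and total transplant columns, none of which depends on the number of doses.

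The protocol defines Group A2 by intention: "Unvaccinated participants who consent to receive 3 doses in Part A (Days 1, 29, and 85" (Table 2). Section 6.2 allows further doses to be withheld for several reasons, among them an adverse event that the investigator judges to require it, and when a participant "Develops, during the course of the study, symptoms or conditions listed in the exclusion criteria". Recent biopsy-proven rejection and suspected rejection are on the transplant exclusion list (4.1.1.2). Participants who are withheld stay in follow-up (5.4).

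The SAP states that it prevails where its methods differ from the protocol (SAP 1). It declares no changes from the protocol (SAP 7).

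**The concern.** A column defined by having received dose 3 admits only people who reached Day 85 and were dosed, yet its events are counted from Day 1. That conditions the early safety record on a later outcome. Three kinds of event before dose 3 are affected:
- An adverse event that prevents dose 2 or dose 3 cannot appear in the 3-dose column, although such events belong to a primary endpoint.
- A death before dose 3 cannot appear there either, although SAP 6.3.1.1 has a row for fatal events.
- A rejection before dose 3 leaves the column whenever it leads to a withheld dose.

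The direction is known: the 3-dose column looks safer than the regimen was. The 2-dose column then mixes people who chose two doses with people whose dosing was stopped.

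**Working it through.** **Plan's own figure.** SAP 4.2 states more than 95% probability of at least one rejection among 200 transplant recipients at a true rate of 3%. 1 − 0.97^200 = 0.9977, so the statement holds. It concerns all transplant recipients together and does not use the regimen columns.

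**Inputs for the 3-dose column**
- p = 3%, the planning rate in SAP 4.2, taken here as the risk over the whole of follow-up (assumption).
- Dose 3 on Day 85 and end of follow-up on Day 450 (Protocol 3.1.1.2): 84 of 449 days precede dose 3.
- w = the share of pre-dose-3 events that stop dosing. The documents give no value; 25% to 100% is assumed.

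**Constant hazard (assumption).** The risk before dose 3 is q = 1 − 0.97^(84/449) = 0.57%. The rate shown in the column is (p − wq)/(1 − wq).

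| w | Rate shown | True rate |
|---|---|---|
| 25% | 2.86% | 3.0% |
| 50% | 2.72% | 3.0% |
| 100% | 2.45% | 3.0% |

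At w = 100%, 0.57/3.0 = 19% of the events leave the column.

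**More events early (assumption).** Let a share s of events precede dose 3, all of them stopping dosing. The column shows (p − sp)/(1 − sp).
- s = 30%: 0.021/0.991 = 2.1%.
- s = 50%: 0.015/0.985 = 1.5%.

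This range is not remote for the Part A stage, which SAP 6.1 closes before the booster. For a booster on Day 205 (Protocol 3.1.1), 84/204 = 41% of the time at risk precedes dose 3.

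**Where the events go.** Take 100 participants planned for three doses (assumed; arm sizes are not in the documents), with constant hazard over 449 days and w = 100%.
- Before Day 29: 100 × (1 − 0.97^(28/449)) = 0.19 expected events, with no specific unvaccinated-transplant regimen column.
- Day 29 to Day 85: 0.57 − 0.19 = 0.38 expected events, moved to the 2-dose column.
- Chance of at least one event before dose 3: 1 − (1 − 0.00568)^100 = 43%.

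**Which columns are affected.** Group A3 receives dose 3 on Day 1, so it has no such selection. The column for all transplant recipients with three doses is affected only through its unvaccinated members. The Overall, kidney, liver and total transplant columns keep every participant and event.

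**The case against.** The strongest reply is that these are only labels. The SAP states no as-received rule, and several places fit planned regimens. SAP 6.2.1 tabulates, by participant group, stopping before dose 2 or dose 3; in a strict 3-doses-received column that row would be empty. SAP 6.5.2 starts counting infections from the last planned dose. SAP 4.1 describes the protocol's groups, and SAP 7 declares no change. This stands as far as it goes: the defect follows from a literal reading, not from an explicit rule. It does not remove the problem. Either the label or the other text is wrong, and two programmers could produce different primary safety tables.

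Four stronger inferences are tempting and are not supported.
- That one-dose participants have no group at all. Overall is itself a dosing-regimen column, and Groups A3 and B4, with one study dose in their part, have named columns. The gap is for unvaccinated transplant recipients stopped after dose 1, and possibly a healthy participant stopped at that point.
- That rejections are lost. The transplant-status columns keep them, and SAP 6.3.1.1 requires separate listings of rejection, serious events and events that stop vaccination.
- That the sample-size statement is undermined. It rests on all transplant recipients, whose rate is the same under either grouping.
- That the 3-dose column would lose most of its events. That needs nearly the whole 3% to fall before Day 85 and every case to be withheld, whereas Protocol 6.2 only permits withholding and follow-up runs to Day 450.

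It is also fair to say that no between-group comparisons are planned (SAP 4.2). The regimen columns are nevertheless the display for a primary objective.

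**Conclusion.** The point holds in a limited form. As labelled, the unvaccinated-transplant regimen columns select on reaching dose 3 while counting events from Day 1. This conflicts with the consent-based arms in Protocol Table 2 and with SAP 6.2.1 and 6.5.2. The SAP needs a rule.

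The bias makes the 3-dose column look safer, and for rejection it is likely to be modest: 2.45% to 2.86% against 3.0% under constant hazard, or 1.5% to 2.1% in the early-event case. These figures rest on the assumed timing of events and the assumed share that stop dosing, neither of which is in the documents. For adverse events that prevent dose 2 or dose 3, and for deaths before dose 3, exclusion from the column is complete under the literal reading, whatever the timing assumption. The all-transplant rejection rate and the detection statement stand.

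**What to change.** In SAP 6.1 and 6.3.1:

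1. Add a safety column for all unvaccinated transplant recipients (Groups A1 and A2, at least one dose). Use it for events from Day 1 to the day before dose 3, or to Day 85 where dose 3 is not given.
2. Report events after dose 3 from the actual date of dose 3, among those who received it.
3. For any regimen column kept from Day 1, state the assignment rule and map the column to Groups A1 to A5. Use the planned regimen only where it was recorded before the events being counted.

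The condition in item 3 matters. Protocol 3.1 says the third dose is offered and describes Group A1 as those who decline it, without saying when that decision is made. If someone declines because of an event after dose 2, assignment by consent would bring the selection back. The pooled column in item 1 avoids this under either reading.

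The cost is SAP wording plus one extra column and period in the adverse event tables. No new data are needed, and no clinical rule changes.

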## 6.2. Background Characteristics

Participant background characteristics will be presented by participant group for the Safety Set, unless otherwise stated.

### 6.2.1. Subject Disposition

The number and percentage of subjects in the following analysis populations will be summarized by participant group as defined in [Section 6.1](#) based on the Safety Set:

- Full Analysis/Safety Set
- mITT (Part A/Part B)

Confidential

- PP Set (Part A/Part B)
- PP Immunogenicity Set (Part A/Part B)
- Solicited Safety Set

Percentages displayed will be based on the number of subjects within each participant group.

The number of subjects in the following categories will be summarized based on subjects screened:

- Number of subjects screened
- Number and percentage of screen failure subjects and the reason for screen failure

The percentage of subjects who screen failed will be based on the number of subjects screened. The reason for screen failure will be based on the number of subjects who screen failed.

The number and percentage of subjects in each of the following disposition categories will be summarized by participant group based on the Safety Set:

- Enrolled into the study by site
- Received each dose of IP
- Prematurely discontinued before receiving the second or third dose of IP and the reason for discontinuation
- Completed study
- Prematurely discontinued the study and the reason for discontinuation

A subject disposition listing will be provided, including informed consent, subjects who completed the study injection schedule, subjects who completed study, subjects who discontinued from study vaccine or who discontinued from participation in the study, with reasons for discontinuation. A separate listing will be provided for screen failure subjects with reasons for screen failure.

A subject who did not receive BD and completed 12 months of follow up after the last injection received is considered to have completed the study. A subject who consented to receive BD and completed 6 months of follow up after the BD is considered to have completed the study.

Confidential

### **6.2.2. Demographics**

Descriptive statistics will be calculated for the following continuous demographic and baseline characteristics: age (years), weight (kg), height (cm), body mass index (BMI) (kg/m^2), and previous vaccination history. Number and percentage of subjects will be provided for categorical variables such as gender, race, ethnicity. The summaries will be presented by participant group as defined in [Section 6.1](#), based on the Safety Set, mITT Set (Part A/Part B), and the PP Immunogenicity Set (Part A/Part B).

For screened failure subjects, age (years), as well as gender, race, ethnicity will be presented in a listing.

In addition, subjects with any inclusion and exclusion criteria violation will also be provided in a listing.

### **6.2.3. Transplant characteristics**

Baseline transplant characteristics, including type of transplant, time since transplant (months), type of donor transplant, indication for transplant, ABO blood group status, and relevant medical history will be summarized for transplant recipients by participant group and presented in a listing.

Relevant medical history for SOT recipients includes history of human leukocyte antigen mismatch, induction therapy, panel reactive antibodies, and prior transplant rejection.

### **6.2.4. Medical History**

Medical history data will be coded by system organ class (SOC) and preferred term (PT) using the Medical Dictionary for Regulatory Activities (MedDRA).

The number and percentage of participants with any medical history will be summarized by SOC and PT based on the Safety Set. A participant will be counted only once for multiple events within each SOC and PT. SOC will be displayed in internationally agreed order. PT will be displayed in descending order of frequency in the overall column, and then alphabetically within SOC.

Medical history data will be presented in a listing.

Confidential

### 6.2.5. Prior and Concomitant Medications

Prior and concomitant medications and non-study vaccination will be coded using the World Health Organization (WHO) drug dictionary (WHODD). Summaries of concomitant medications will be based on the Safety Set. Prior medications are defined as those reported medications that are taken prior to the first study injection. For SOT participants, prior immunosuppressants received within 3 months prior to the first study injection will be included. Concomitant medications are defined as those medications that are taken from the time of any injection through the following 28 days following the injection. In this manner, a medication can be both prior and concomitant. For SOT participants, concomitant immunosuppressant medications, including but not limited to, glucocorticoids, immunophilin binding agents, and inhibitors of de novo nucleotide synthesis within 28 days prior to the first study injection and throughout the study, and any immunosuppressants listed in the exclusion criteria if taken during the study will be included. The handling of missing or partial start and end dates for medications is described in [Appendix C](#). The number and percentage of subjects using concomitant medications and non-study vaccination during the 7-day follow-up period (i.e., on the day of injection and the 6 subsequent days) and during the 28-day follow-up period after each injection (i.e., on the day of injection and the 27 subsequent days) will be summarized by participant group as defined in [Section 6.1](#) and as follows:

- Any concomitant medications and non-study vaccination within 7 days post-injection
- Any concomitant medications and non-study vaccination within 28 days post-injection
- Seasonal influenza vaccine within 28 days post-injection
- Antipyretic or analgesic medication within 28 days post-injection

Medications taken to prevent pain or fever will be collected on eDiary and summaries will be provided based on each of the Solicited Safety Sets by participant group as defined in [Section 6.1](#) for each injection (first, second, third, or BD) and for any injection.

A separate summary table of the number and percentage of subjects using concomitant immunosuppressive medications will be summarized by participant group and presented by PT. In addition, a summary table will be provided for the number and percentage of subjects who experienced any change in immunosuppressant therapy from Day 1 through

Confidential

the end of the study by participant group. Immunosuppressive medications, including any change in immunosuppressant therapy, the description of this change, and the reason for this change will be presented in a separate listing.

Prior and concomitant medications and non-study vaccinations will be presented in a listing.

Concomitant procedures will be presented in a listing.

